HCC	Hepatocellular carcinoma
IB	Investigator's Brochure
ICF	Informed Consent Form
IHC	Immunohistochemistry
IP	Investigational Product
IV	Intravenous
LFTs	Liver function tests
LLN	Lower limit of normal
MRI	Magnetic Resonance Imaging
ORR	Overall Response Rate
OS	Overall Survival
PD	Progressive Disease
PFS	Progression-Free Survival
PI	Principal Investigator
PR	Partial Response
PS	Performance Status
RNA	Ribonucleic Acids
SAE	Serious adverse event
SD	Stable disease
SUSAR	Suspected unexpected serious adverse reaction
TSH	Thyroid Stimulating Hormone
ULN	Upper limit of normal
WBC	White blood cell count

CONFIDENTIAL

Study Summary

Title	Phase II Trial of Abemaciclib and Nivolumab for Subjects with Hepatocellular Carcinoma
Short Title	Abemaciclib and Nivolumab for HCC
IRB Number	Pending
Protocol Number	Pending
Phase	Phase II
Methodology	Single-arm open-label
Study Duration	24 months (18 months for accrual and 6 additional months for follow-up)
Study Center(s)	University of Pennsylvania Abramson Cancer Center
Objectives	
Primary:
 
• To determine the overall response rate 
Secondary:
 
• To determine progression-free survival, duration of response, and overall survival• To determine toxicity 
Exploratory:
 
• To explore potential biomarkers of anti-tumor immunity in peripheral blood and paired tissue biopsies
Number of Subjects	27 evaluable

CONFIDENTIAL

This material is the property of the University of Pennsylvania.

Main Inclusion and Exclusion Criteria	
1. Advanced HCC with histologic confirmation2. Retinoblastoma (RB) positive by immunohistochemistry3. ECOG PS 0 or 14. Childs-Pugh A or B75. ANC $\geq 1500 \times 10^9/L$6. Platelets $\geq 75,000 \times 10^9/L$7. No prior therapy with a PD-1, PD-L1, or CDK4/6 inhibitor8. No uncontrolled ascites9. No esophageal varices requiring treatment in the past 6 months10. No serious autoimmune disease, interstitial lung disease, or solid organ transplant11. No use of systemic corticosteroids other than for adrenal hormone replacement
Investigational Product	Abemaciclib 150mg by mouth twice daily
Duration of administration	Until progression, intolerance, or withdrawal of consent
Reference therapy	Historic results from nivolumab in HCC
Statistical Methodology	
Primary endpoint will be overall response rate (ORR) by RECIST v. 1.1. This will be compared to historical ORR with nivolumab. Toxicity rates will be calculated using CTCAE v. 5.0. Kaplan-Meier methods will be used to calculate PFS, DOR, and OS using RECIST v. 1.1 and iRECIST criteria
 
With 27 subjects, a one-sided binomial test with alpha = 0.10 will have 81% power to detect an improvement in ORR from 18% (H0) to 36% (H1).

CONFIDENTIAL

This material is the property of the University of Pennsylvania.

BACKGROUND AND STUDY RATIONALE

This study will be conducted in full accordance all applicable University of Pennsylvania Research Policies and Procedures and all applicable Federal and state laws and regulations.

1 Introduction

Hepatocellular carcinoma is the second leading cause of cancer deaths worldwide, resulting in an estimated 810,000 deaths in 2015 [1]. Even as deaths from other common cancers have declined in the United States, mortality from HCC has doubled in the past two decades, and HCC is now the fifth-leading cause of cancer deaths in the U.S. [2]. For patients with advanced HCC not amenable to ablation, surgical resection, or transplant, median survival is less than one year. The accelerated approval of the PD-1 inhibitor nivolumab by the FDA in 2017 illustrates the benefit of immunotherapy for advanced HCC, but, with an overall response rate (ORR) of only 15-20% in studies of pembrolizumab and nivolumab in HCC, more effective combinations are clearly needed [3, 4].

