4.1 Inclusion Criteria

1. Subjects must have hepatocellular carcinoma (HCC) that is inoperable (where surgery is not indicated due to disease extent, co-morbidities, or other technical reasons)
2. Histologic confirmation of HCC is not required for screening but is required prior to initiation of study treatment. Subjects with hepatocholangiocarcinoma or cholangiocarcinoma are not eligible.
3. Tumor must be positive for retinoblastoma (RB) expression by immunohistochemistry
4. Age \geq 18 years and ability to understand and the willingness to sign a written informed consent document.
5. ECOG performance status of 0 or 1
6. Childs-Pugh score of ≤ 7
7. Life expectancy of at least 12 weeks
8. Must be able to swallow tablets
9. Must be willing to comply with protocol procedures (including completion of diaries and outcome measures)
10. Local or loco-regional therapy to the liver (i.e. surgery, radiation therapy, hepatic arterial embolization, chemoembolization, radiofrequency ablation, percutaneous ethanol injection, or cryoablation) must have been completed ≥ 4 weeks prior to enrollment
11. Must be willing to undergo a pretreatment and on-treatment biopsy and have a tumor site that is accessible for core needle biopsy
12. Measurable or evaluable disease as defined by RECIST v. 1.1
13. Women of childbearing potential must have a negative serum pregnancy test performed within 7 days of the first dose of abemaciclib (see Appendix A for definition of childbearing potential). Female subjects of childbearing potential must use an approved contraceptive method (detailed in Appendix A) for the duration of the study and an additional 3 weeks after the final dose of abemaciclib.
14. Subjects with hepatitis B must have an HBV viral load < 100 IU/mL by PCR during screening
15. Must have adequate organ and hematopoietic function as defined below:

Table 5: Baseline Laboratory Parameters

Laboratory Test	Required Value
Absolute neutrophil count (ANC)	$\geq 1.5 \times 10^9/L$
Platelet count	$\geq 75,000 \times 10^9/L$
Hemoglobin	$\geq 8.0 \times 10^9/L$

CONFIDENTIAL

This material is the property of the University of Pennsylvania.

Alanine aminotransferase (ALT)	$\leq 3 \times \text{ULN}$
Aspartate aminotransferase (AST)	$\leq 3 \times \text{ULN}$
Serum creatinine	$\leq 1.5 \times \text{ULN}$
OR creatinine clearance (CrCl)	OR $\text{CrCl} \geq 50 \text{mL/min}$ by Cockcroft-Gault Formula
Total bilirubin	$\leq 2.0 \times \text{ULN}$
Serum albumin	$\geq 2.8 \text{ g/dL}$

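### Three blood-count entry limits are contradictory or unusable as written: the ANC limit differs 1000-fold between the synopsis and section 4.1, the platelet limit is an impossible count in both, and the hemoglobin limit is in a cell-count unit

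*Combined protocol and SAP*

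**What the plan says.** The Study Summary, under Main Inclusion and Exclusion Criteria, lists "ANC $\geq 1500 \times 10^9/L" and "Platelets $\geq 75,000 \times 10^9/L". It gives no hemoglobin limit.

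The full criteria are in section 4.1. Inclusion criterion 15 reads "Must have adequate organ and hematopoietic function as defined below" and points to a table of baseline laboratory parameters. The table is numbered 5, a number also used for the pneumonitis table in section 3.1.1; here Table 5 always means the one in section 4.1. It sets these lower limits:

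- ANC: 1.5 x 10^9/L
- Platelets: 75,000 x 10^9/L
- Hemoglobin: 8.0 x 10^9/L

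Serum albumin, in the same table, has a limit of 2.8 g/dL. Section 7.7 and the footnotes to the schedule of procedures list the blood count components without limits or units. The dose modification rules in section 3.1.1 work by CTCAE grade and do not restate the entry limits.

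**The concern.** An eligibility limit is a decision threshold. Someone screening a subject, or auditing that decision later, should be able to set the laboratory result against the approved text and get one answer. Here the three blood counts fail that test in three different ways. The ANC limit has two values. The platelet limit has one value, but no one could reach it. The hemoglobin limit has a numeral with a unit that does not measure hemoglobin.

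These are operative entry limits. Section 1.2.1.2 reports neutropenia, anemia and thrombocytopenia with abemaciclib, and the protocol calls for tumor biopsies at baseline and on days 15 to 19 of cycle 1 (section 7.11.2 allows omission in the subject's interest). For platelets and hemoglobin the faulty entry is in criterion 15 itself, so preferring the body of the protocol over the synopsis does not resolve it.

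**Working it through.** The plan has no calculated figure to reproduce on this point. The check is unit arithmetic on the printed limits, using 1 litre = 10^6 microlitres.

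| Limit | Synopsis | Section 4.1, Table 5 |
|---|---|---|
| ANC | 1500 x 10^9/L | 1.5 x 10^9/L |
| Platelets | 75,000 x 10^9/L | 75,000 x 10^9/L |
| Hemoglobin | not given | 8.0 x 10^9/L |

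**ANC.**
- Synopsis: 1500 x 10^9 / 10^6 = 1,500,000 per microlitre.
- Table 5: 1.5 x 10^9 / 10^6 = 1,500 per microlitre.
- Ratio: 1500 / 1.5 = 1000.

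The Table 5 limit is attainable and in a valid unit, so for ANC the fault is a contradiction between the two places.

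**Platelets.**
- Both places: 75,000 x 10^9 = 7.5 x 10^13 per litre.
- 7.5 x 10^13 / 10^6 = 75,000,000 per microlitre.

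To see whether this could occur, assume a platelet volume of 7 to 12 fL (an assumption; the documents give none). The share of blood volume taken up by platelets would be:

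- at 7 fL: 7.5 x 10^13 x 7 x 10^-15 = 0.525, about 53%;
- at 12 fL: 7.5 x 10^13 x 12 x 10^-15 = 0.90, or 90%.

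The count is impossible across that range.

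**Hemoglobin.** A value in 10^9/L is a number of particles per litre, and hemoglobin is measured as a concentration. A laboratory result cannot be called above or below 8.0 x 10^9/L, so the limit is neither too high nor too low: it cannot be evaluated. The albumin row shows that the table can carry a mass unit.

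**Likely origin.** Read per microlitre, the synopsis ANC numeral equals the Table 5 limit: 1500 x 10^6 = 1.5 x 10^9 per litre. The same reading of the platelet numeral gives 75,000 x 10^6 = 75 x 10^9 per litre. Per-microlitre numerals attached to a per-litre unit would therefore explain the synopsis ANC entry and both platelet entries. It would not explain the hemoglobin entry. This is an inference from the numerals; the documents do not state it.

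**Effect on the design.** The limits do not enter the sample size calculation. As a side check, an exact one-sided binomial test with n = 27, declaring success at 8 or more responses, has a type I error of 0.0977 at 18% and power of 0.812 at 36%. That agrees with the stated 81% power at a one-sided alpha of 0.10.

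**The case against.** The strongest reply is that nobody would apply these limits literally. Experienced staff would recognise the slips, and the document itself shows how the ANC numerals agree. This is a single center with two enrolling locations (section 4.4), and section 11.1 has the Medical Monitor consulted on eligibility. No endpoint, test or estimate changes, and no wrong enrolment is shown. On that view this is an editorial correction. Most of this stands, and it limits the practical effect. It does not supply a valid platelet or hemoglobin limit, because neither is stated correctly anywhere in the documents.

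A second reply is that the PDF reading may have altered the table. That is unlikely for platelets, where the same expression appears in two separate places. It is harder to exclude for hemoglobin, whose unit appears once, directly below two rows ending in the same unit. A look at the source file would settle it.

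Three stronger readings are tempting and should not be drawn:

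- **That all three limits shut subjects out.** In section 4.1 only the platelet row makes literal eligibility zero. The ANC limit there can be met, and the hemoglobin limit cannot be evaluated. Nor does it follow that every enrolment would in practice be treated as a departure from the criteria.
- **That the committee could reject each enrolment as an eligibility exception.** Section 9.6 defines an exception as a one-time, intentional, prospectively planned departure. A printed unit error affecting everyone is not that, and the same section requires a protocol amendment where a situation is likely to recur.
- **That the case report form checks are wrong or inconsistent.** The forms and their range checks are not in these documents, so nothing can be said about them.

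**Conclusion.** The point holds as a defect in the operative eligibility text. ANC differs by a factor of exactly 1000 between the synopsis and Table 5; platelets are set at 75 million per microlitre in both; hemoglobin has no evaluable limit. The ANC ratio and the platelet conversion follow directly from the printed numbers. The judgment that the platelet count is impossible was illustrated with an assumed platelet volume, and it does not depend on where in the 7 to 12 fL range that volume lies.

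The consequence is confined to verification: screening decisions, internal audit and any later check of who was eligible have to rely on an inferred limit. The conclusion rests on two assumptions: that the text as read matches the source PDF, and that no corrected version of the limits exists outside these documents. The correction is worth making because it concerns entry criteria and costs almost nothing.

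**What to change.** In the next amendment, reconcile the synopsis list with Table 5 of section 4.1. State each limit with the same numeral and a valid unit wherever it appears: one count unit for both ANC and platelets, and a concentration unit for hemoglobin. Before the change is made, the sponsor should check the source PDF and confirm the intended value of each limit; this review proposes none.

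The cost is a handful of corrected entries in two places. The sample size, endpoints and analysis stay as they are.

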1.1 Background and Relevant Literature

Recent preclinical studies have demonstrated potentiation of anti-tumor immunity and increases in tumor-infiltrating lymphocytes by CDK4/6 inhibitors as well as synergy between PD-1 and CDK4/6 inhibitors [5-8]. Mechanisms demonstrated have included inhibition of proliferation of regulatory T cells (Treg), enhanced antigen presentation and type III interferon production, decreased PD-L1 degradation, decreases in myeloid-derived suppressor cells (MDSCs), and increased IL-2 production due to derepression of nuclear factor of activated T cells (NFAT) pathways. Improvement in response has been shown with an initial 7-day run-in of abemaciclib prior to PD-L1 therapy compared to concurrent or sequential administration [9]. Additionally, single agent activity of CDK4/6 inhibitors has been demonstrated in RB-positive HCC, which account for about 70% of tumors, with impaired tumor growth and improved survival in murine models [10]. A single-arm phase II trial of palbociclib showed a median progression-free survival of nearly 6 months, but the clinical efficacy of CDK4/6 inhibitors has never been further explored in a randomized study in HCC [11]. As a single agent in HCC, nivolumab has demonstrated an overall response rate of 15-20% [3] and received accelerated approval from the FDA in HCC based on the results of the Checkmate-040.

We hypothesize that the addition of abemaciclib to nivolumab in advanced HCC will double the overall response rate (ORR) compared to nivolumab alone by both enhancing anti-tumor immunity and inhibiting cell cycle progression.

Ongoing studies in breast cancer and non-small cell lung cancer have demonstrated the safety of abemaciclib and pembrolizumab at standard doses, and it is assumed that the combination of abemaciclib and nivolumab will be similarly tolerable in an HCC population [12]. This will be a single-arm phase II trial to test the initial efficacy of this combination and elucidate the immune effects of abemaciclib in HCC.

1.2 Name and Description of the Investigational Product

Abemaciclib is an oral inhibitor of cyclin-dependent kinases 4 and 6 (CDK4 and CDK6). These kinases are activated upon binding to D-cyclins. Cyclin D1 and CDK4/6 promote phosphorylation of the retinoblastoma protein (Rb), cell cycle progression, and cell proliferation. In vitro, continuous exposure to abemaciclib inhibited Rb phosphorylation and blocked progression from G1 into S phase of the cell cycle, resulting in senescence and apoptosis.

1.2.1 Clinical Data to Date

1.2.1.1 Human Pharmacokinetics

The pharmacokinetics of abemaciclib were characterized in patients with solid tumors, including metastatic breast cancer, and in healthy subjects. Following single and repeated twice daily dosing of 50 mg (0.3 times the approved recommended 150 mg dosage) to 200 mg of abemaciclib, the increase in plasma exposure (AUC) and Cmax was approximately dose proportional. Steady state was achieved within 5 days following

CONFIDENTIAL

repeated twice daily dosing, and the estimated geometric mean accumulation ratio was 2.3 (50% CV) and 3.2 (59% CV) based on Cmax and AUC, respectively.

Absorption

The absolute bioavailability of abemaciclib after a single oral dose of 200 mg is 45% (19% CV). The median Tmax of abemaciclib is 8.0 hours (range: 4.1-24.0 hours).

Effect of Food

A high-fat, high-calorie meal (approximately 800 to 1000 calories with 150 calories from protein, 250 calories from carbohydrate, and 500 to 600 calories from fat) administered to healthy subjects increased the AUC of abemaciclib plus its active metabolites by 9% and increased Cmax by 26%.

Distribution

In vitro, abemaciclib was bound to human plasma proteins, serum albumin, and alpha-1-acid glycoprotein in a concentration independent manner from 152 ng/mL to 5066 ng/mL. In a clinical study, the mean (standard deviation, SD) bound fraction was 96.3% (1.1) for abemaciclib, 93.4% (1.3) for M2, 96.8% (0.8) for M18, and 97.8% (0.6) for M20. The geometric mean systemic volume of distribution is approximately 690.3 L (49% CV). In patients with advanced cancer, including breast cancer, concentrations of abemaciclib and its active metabolites M2 and M20 in cerebrospinal fluid are comparable to unbound plasma concentrations.

Elimination

The geometric mean hepatic clearance (CL) of abemaciclib in patients was 26.0 L/h (51% CV), and the mean plasma elimination half-life for abemaciclib in patients was 18.3 hours (72% CV).

Metabolism: Hepatic metabolism is the main route of clearance for abemaciclib. Abemaciclib is metabolized to several metabolites primarily by cytochrome P450 (CYP) 3A4, with formation of N-desethylabemaciclib (M2) representing the major metabolism pathway. Additional metabolites include hydroxyabemaciclib (M20), hydroxy-N-desethylabemaciclib (M18), and an oxidative metabolite (M1). M2, M18, and M20 are equipotent to abemaciclib and their AUCs accounted for 25%, 13%, and 26% of the total circulating analytes in plasma, respectively.

Excretion: After a single 150 mg oral dose of radiolabeled abemaciclib, approximately 81% of the dose was recovered in feces and approximately 3% recovered in urine. The majority of the dose eliminated in feces was metabolites.

Specific Populations

Age, Gender, and Body Weight Based on a population pharmacokinetic analysis in patients with cancer, age (range 24-91 years), gender (134 males and 856 females), and body weight (range 36-175 kg) had no effect on the exposure of abemaciclib.

Patients with Renal Impairment: In a population pharmacokinetic analysis of 990 individuals, in which 381 individuals had mild renal impairment ($60 \text{ mL/min} \leq \text{CLcr} < 90 \text{ mL/min}$) and 126 individuals had moderate renal impairment ($30 \text{ mL/min} \leq \text{CLcr} < 60 \text{ mL/min}$), mild and moderate renal impairment had no effect on the exposure of abemaciclib. The effect of severe renal impairment ($\text{CLcr} < 30 \text{ mL/min}$) on pharmacokinetics of abemaciclib is unknown.

Patients with Hepatic Impairment: Following a single 200 mg oral dose of abemaciclib, the relative potency adjusted unbound AUC 0-INF of abemaciclib plus its active metabolites (M2, M18, M20) in plasma increased 1.2-fold in subjects with mild hepatic impairment (Child-Pugh A, n=9), 1.1-fold in subjects with moderate hepatic impairment (Child-Pugh B, n=10), and 2.4-fold in subjects with severe hepatic impairment (Child-Pugh C, n=6) relative to subjects with normal hepatic function (n=10). In subjects with severe hepatic impairment, the mean plasma elimination half-life of abemaciclib increased to 55 hours compared to 24 hours in subjects with normal hepatic function.

CONFIDENTIAL

This material is the property of the University of Pennsylvania.

Drug Interaction Studies

Effects of Other Drugs on Abemaciclib

Strong CYP3A Inhibitors:

- Ketoconazole (a strong CYP3A inhibitor) is predicted to increase the AUC of abemaciclib by up to 16-fold.
- Itraconazole (a strong CYP3A inhibitor) is predicted to increase the relative potency adjusted unbound AUC of abemaciclib plus its active metabolites (M2, M18 and M20) by 2.2-fold.
- Coadministration of 500 mg twice daily doses of clarithromycin (a strong CYP3A inhibitor) with a single 50 mg dose of abemaciclib (0.3 times the approved recommended 150 mg dosage) increased the relative potency adjusted unbound AUC 0-INF of abemaciclib plus its active metabolites (M2, M18, and M20) by 1.7-fold relative to abemaciclib alone in cancer patients.

Moderate CYP3A Inhibitors:

- Diltiazem and verapamil (moderate CYP3A inhibitors) are predicted to increase the relative potency adjusted unbound AUC of abemaciclib plus its active metabolites (M2, M18, and M20) by 1.7-fold and 1.3-fold, respectively.

Strong CYP3A Inducers:

- Coadministration of 600 mg daily doses of rifampin (a strong CYP3A inducer) with a single 200 mg dose of VERZENIO decreased the relative potency adjusted unbound AUC0-INF of abemaciclib plus its active metabolites (M2, M18, and M20) by 67% in healthy subjects.

Moderate CYP3A Inducers:

- The effect of moderate CYP3A inducers on the pharmacokinetics of abemaciclib is unknown.

Loperamide:

- Co-administration of a single 8-mg dose of loperamide with a single 400-mg dose of abemaciclib in healthy subjects increased the relative potency adjusted unbound AUC0-INF of abemaciclib plus its active metabolites (M2 and M20) by 12%, which is not considered clinically relevant.

Fulvestrant:

- In clinical studies in patients with breast cancer, fulvestrant had no clinically relevant effect on the pharmacokinetics of abemaciclib or its active metabolites.
-

Effects of Abemaciclib on Other Drugs

Loperamide:

- In a clinical drug interaction study in healthy subjects, coadministration of a single 8 mg dose of loperamide with a single 400 mg abemaciclib (2.7 times the approved recommended 150 mg dosage) increased loperamide AUC0-INF by 9% and Cmax by 35% relative to loperamide alone. These increases in loperamide exposure are not considered clinically relevant.

Metformin:

- In a clinical drug interaction study in healthy subjects, coadministration of a single 1000 mg dose of metformin, a clinically relevant substrate of renal OCT2, MATE1, and MATE2-K transporters, with a single 400 mg dose of abemaciclib (2.7 times the approved recommended 150 mg dosage) increased metformin AUC0-INF by 37% and Cmax by 22% relative to metformin alone. Abemaciclib reduced the renal clearance and renal secretion of metformin by 45% and 62%, respectively, relative to metformin alone, without any effect on glomerular filtration rate (GFR) as measured by iohexol clearance and serum cystatin C.

Fulvestrant:

- In clinical studies in patients with breast cancer, abemaciclib had no clinically relevant effect on fulvestrant pharmacokinetics.

In Vitro Studies

CONFIDENTIAL

This material is the property of the University of Pennsylvania.

Transporter Systems:

Abemaciclib and its major active metabolites inhibit the renal transporters OCT2, MATE1, and MATE2-K at concentrations achievable at the approved recommended dosage. The observed serum creatinine increase in clinical studies with abemaciclib is likely due to inhibition of tubular secretion of creatinine via OCT2, MATE1, and MATE2-K. Abemaciclib and its major metabolites at clinically relevant concentrations do not inhibit the hepatic uptake transporters OCT1, OATP1B1, and OATP1B3 or the renal uptake transporters OAT1 and OAT3.

Abemaciclib is a substrate of P-gp and BCRP. Abemaciclib and its major active metabolites, M2 and M20, are not substrates of hepatic uptake transporters OCT1, organic anion transporting polypeptide 1B1 (OATP1B1), or OATP1B3.

Abemaciclib inhibits P-gp and BCRP. The clinical consequences of this finding on sensitive P-gp and BCRP substrates are unknown.

CYP Metabolic Pathways:

Abemaciclib and its major active metabolites, M2 and M20, do not induce CYP1A2, CYP2B6, or CYP3A at clinically relevant concentrations. Abemaciclib and its major active metabolites, M2 and M20, downregulate mRNA of CYPs, including CYP1A2, CYP2B6, CYP2C8, CYP2C9, CYP2D6 and CYP3A4. The mechanism of this down regulation and its clinical relevance are not understood. However, abemaciclib is a substrate of CYP3A4, and time-dependent changes in pharmacokinetics of abemaciclib as a result of autoinhibition of its metabolism was not observed.

P-gp and BCRP Inhibitors:

In vitro, abemaciclib is a substrate of P-gp and BCRP. The effect of P-gp or BCRP inhibitors on the pharmacokinetics of abemaciclib has not been studied.

